4.1. SCREENING PHASE

The subject (or Legally Acceptable Representative (LAR)) will sign and date the informed consent form (ICF) and Health Insurance Portability Accountability Act (HIPAA) authorization (according to site policy and practices) prior to any study-related procedures. All study centers will be instructed to maintain the study-specific screening and enrollment logs at their sites. If a subject initially fails to meet inclusion/exclusion criteria and is later reconsidered for participation, the subject will be re-consented and assigned a new unique identification number at the time of rescreening. Subjects who fail their first screening attempt may be re-screened a maximum of once and may be enrolled if they are found to meet all inclusion and no exclusion criteria when rescreened.

4.1.1. Screening Visit (V1)

After the ICF has been signed, screening procedures and information will be obtained to confirm subject eligibility, including:

- Demographic information (see Section 7.3);
- A detailed medical history (see Section 7.4);
- Physical examination (see Section 7.5);
- Vital signs (see Section 7.6),
- Pulse oxygen saturation (SpO2) (See Section 7.10)
- 12-lead electrocardiogram (see Section 7.11);
- Clinical Symptom Score Assessment (see Section 7.14)
- Collection of laboratory specimens (see Section 7.8) for
 - Complete blood count;
 - o Biochemistry;
 - Coagulation indices;
 - o Urine pregnancy test, for female subjects of childbearing potential; and
 - o Urine sample for urinalysis parameters.
- Prior and concomitant medications assessment (see Section 7.7).

All screening information will be fully documented in the subject's medical records (i.e., source documents).

CONFIDENTIAL Page 49 of 101

- For consented subjects who do not meet eligibility criteria, a Screen Failure Case Report Form (CRF) will be completed. The Screen Failure CRF will contain the following details: the subject identification number, the date of ICF signature, demographic information (see Section 7.3), and the reason for screen failure. No additional information will be required for subjects who fail screening.
- For consented subjects who meet eligibility criteria, all required screening information will be transcribed onto the appropriate page of the CRF.

4.2. TREATMENT PHASE

Subjects who meet all eligibility criteria, as per data gathered from Screening Period are to be treated. All subjects who fail to meet eligibility criteria will be considered screen failure and will exit the study without further evaluation

4.2.1. Visit 2 (V2)

The following assessments will be performed at the first treatment visit prior to the first treatment administration. If Visit 2 (V2) takes place on the same day as the Screening Visit (V1), scheduled assessments performed under screening (V1) do not need to be repeated at V2.

- Physical examination (see Section 7.5);
- Vital Signs (see Section 7.6),
- Pulse oxygen saturation (SpO2) (see Section 7.10);
- Clinical Symptom Score Assessment (see Section 7.14)
- PROMIS® Fatigue Scale (see Section 7.16);
- PROMIS® Cognitive Function(see Section 7.17);
- PROMIS® Sleep Disturbance (see Section 7.18);
- Collection of blood specimens (see Section 7.8) for
 - o CD4+ and CD8+ T cell count;
 - Serum cytokine and chemokine levels;
 - o CCR5 receptor occupancy;
 - o Immunophenotypic biomarker analysis.
- Urine pregnancy test, for female subjects of childbearing potential

Subjects will be randomized 1:1 via WebView CTMS system to Leronlimab (PRO 140) or Placebo (see Section 7.13).

CONFIDENTIAL Page 50 of 101

• Leronlimab (PRO 140) 700 mg or

Placebo

Leronlimab (PRO 140) or placebo will be administered subcutaneously to all subjects at a weekly dose of 700 mg. After receiving the first leronlimab (PRO 140) dose, the following assessments will be performed:

- Vital signs (see Section 7.6),
- Pulse oxygen saturation (SpO2) (see Section 7.10),
- Concomitant medications assessment (see Section 7.7),
- Review of adverse events (see Section 9)

4.2.2. Visits 3, 5, 7, 9, 11, 13, and 15 (V3, V5, V7, V9, V11, V13, and V15)

Telephone or video contact visits will be performed 3 days (± 1 day) after each treatment administration visit. The following assessments will be performed:

- Patient Symptom Diary (see Section 7.15);
 Note: Patient compliance to daily diary completion will be checked by site staff.
- Assessment for the requirement of hospitalization (see Section 7.12);
- Prior and concomitant medications assessment (see Section 7.7); and
- Review of adverse events (see Section 9).

4.2.3. Visits 4, 6, 8, 10, 12, 14, and 16 (V4, V6, V8, V10, V12, V14, and V16)

The following assessments will be performed:

- Physical examination (see Section 7.5);
- Vital Signs (see Section 7.6),
- Pulse oxygen saturation (SpO2) (see Section 7.10);
- Patient Symptom Diary (see Section 7.15);

Note: Patient compliance to daily diary completion will be checked by site staff.

- PROMIS® Fatigue Scale (see Section 7.16);
- PROMIS® Cognitive Function (See Section 7.17);
- PROMIS® Sleep Disturbance (see Section 7.18);
- Collection of laboratory specimens at V10 only (see Section 7.8) for

CONFIDENTIAL Page 51 of 101

Complete blood count;

- Biochemistry;
- Coagulation indices;
- o Urine sample for urinalysis parameters;
- o CD4+ and CD8+ T cell count;
- Serum cytokine and chemokine levels;
- o CCR5 receptor occupancy; and
- o Immunophenotypic biomarker analysis.
- Urine pregnancy test, for female subjects of childbearing potential V10 only
- Leronlimab (700 mg) or Placebo Administration
- Assessment for the requirement of hospitalization (see Section 7.12);
- Prior and concomitant medications assessment (see Section 7.7); and
- Review of adverse events (see Section 9).

4.2.4. End of Treatment – EOT (V17)

The last visit during the treatment phase will be considered at the End of Treatment (EOT) visit. The assessments performed at this visit will include:

- Physical examination (see Section 7.5);
- Vital Signs (see Section 7.6),
- Pulse oxygen saturation (SpO2) (see Section 7.10);
- 12-lead electrocardiogram (see Section 7.11);
- Patient Symptom Diary (see Section 7.15);

Note: Patient compliance to daily diary completion will be checked by site staff.

- PROMIS® Fatigue Scale (see Section 7.16);
- PROMIS® Cognitive Function (see Section 7.17);
- PROMIS® Sleep Disturbance (see Section 7.18);
- Global Health Assessment (see Section 7.19);
- Collection of laboratory specimens (see Section 7.8) for
 - Complete blood count;

CONFIDENTIAL Page 52 of 101

- Biochemistry;
- Coagulation indices;
- O Urine pregnancy test, for female subjects of childbearing potential;
- Urine sample for urinalysis parameters;
- o CD4+ and CD8+ T cell count;
- Serum cytokine and chemokine levels;
- o CCR5 receptor occupancy; and
- Immunophenotypic biomarker analysis.
- Assessment for the requirement of hospitalization (see Section 7.12);
- Prior and concomitant medications assessment (see Section 7.7); and
- Review of adverse events (see Section 9).

4.3. FOLLOW-UP PHASE

The follow-up visit is scheduled $28(\pm 3)$ days after EOT Visit.

4.3.1. Visit 18

The assessments performed at these visits will include:

- Vital Signs (see Section 7.6),
- Pulse Oxygen Saturation (see Section 7.10)
- Physical examination (see Section 7.5);
- Collection of blood specimens (see Section 7.8) for
 - o Immunophenotypic biomarker analysis
- Assessment for the requirement of hospitalization (see Section 7.12);
- Prior and concomitant medications assessment (see Section 7.7); and
- Review of adverse events (see Section 9).

4.4. UNSCHEDULED VISITS

In the event that the subject will return to clinic at a time other than a regularly scheduled study visit, the visit will be regarded as an unscheduled visit. Assessments at unscheduled visits are at the discretion of the Investigator. All pertinent findings, including adverse events or changes in medications, will be noted in the eCRF.

CONFIDENTIAL Page 53 of 101

5. SUBJECT COMPLETION, WITHDRAWAL AND CRITERIA FOR STOPPING THE STUDY

5.1. SUBJECT COMPLETION

A subject is considered to have completed the study once all follow-up visit assessments have been completed.

5.2. EARLY STOPPING RULES

Upon occurrence of any of the following events, data will be reviewed by the Medical Monitor and the Lead Principal Investigator.

- 1. Death in any subject in which the cause of death is judged to be probably or definitely related to the study drug by the treating investigator;
- 2. The occurrence in any subject of a life-threatening SAE whose causal relationship to study drug is judged to be probable or definite by the treating investigator;
- 3. Two (2) occurrences of Grade 4 toxicities that are assessed to be probably or definitely related to the study drug by the treating investigator;
- 4. Two (2) occurrences of a Grade 2 or higher allergic/hypersensitivity reaction directly related to the study drug that lead to permanent discontinuation of study drug.

In case the above listed event(s) occurred, patient accrual will be suspended pending further review and the FDA and other global regulatory authority will be notified. The study will be stopped if any of these stopping criteria are met unless, after reviewing the safety events of interest, the medical monitor and Sponsor, agree to allow the study to proceed. The FDA and other global regulatory authority will be consulted for any protocol amendment before restarting the trial if a stopping rule is met.

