9.2.3. Causality Assessment

AEs will be assigned a relationship (causality) to the study treatment. The Investigator will be responsible for determining the relationship between an AE and the study treatment. The type of event, organ system affected, and timing of onset of the event will be factors in assessing the likelihood that an AE is related to the study treatment. Relationship of AEs to study treatment will be classified as follows:

- 1. Definitely related: This category applies to those AEs that the Investigator feels are incontrovertibly related to the study treatment. An AE may be assigned an attribution of definitely related if or when it meets all of the following criteria: (1) it follows a reasonable temporal sequence from administration of the study treatment; (2) it could not be reasonably explained by the known characteristics of the subject's clinical state, environmental or toxic factors, or other modes of therapy administered to the subject; (3) it follows a known response pattern to treatment with the study treatment.
- 2. Probably related: This category applies to those AEs which, after careful medical consideration at the time they are evaluated, are felt with a high degree of certainty to be related to the study treatment. An AE may be considered probable if or when (must have three): (1) it follows a reasonable temporal sequence from administration of the study treatment. (2) It could not readily have been produced by subject's clinical state, environmental or toxic factors, or other therapies administered to the subject. (3) Disappears or is decreased upon discontinuation of the study treatment. (4) It follows a known response pattern to treatment with the study

CONFIDENTIAL Page 76 of 101

[†]Self care ADL refer to bathing, dressing and undressing, feeding self, using the toilet, taking medications, and not bedridden.

treatment.

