- 3. Possibly related: This category applies to those AEs which, after careful medical consideration at the time they are evaluated, are judged unlikely but cannot be ruled out with certainty to the study treatment. An AE may be considered possible if or when (must have two): (1) it follows a reasonable temporal sequence from administration of the study treatment. (2) It could not readily have been produced by subject's clinical state, environmental or toxic factors, or other therapies administered to the subject. (3) Disappears or is decreased upon discontinuation of the study treatment. (4) It follows a known response pattern to treatment with the study treatment.
- **4.** Unlikely related: In general this category can be considered applicable to those AEs which, after careful medical consideration at the time they are evaluated, are judged likely to be unrelated to the study treatment. An AE may be considered unlikely if or when (must have two): (1) it does not follow a reasonable temporal sequence from administration of the study treatment. (2) It could not readily have been produced by subject's clinical state, environmental or toxic factors, or other therapies administered to the subject. (3) Disappears or is decreased upon discontinuation of the study treatment. (4) It does not follow a known response pattern to treatment with the study treatment.
- **5.** Unrelated: This category applies to those AEs which, after careful consideration at the time they are evaluated, are clearly and incontrovertibly due to extraneous causes (disease, environment, etc.) and determined with certainty to have no relationship to the study treatment.

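### If the causality counts in Section 9.2.3 are followed, a drug-related death can fall short of stopping rule 1 for want of evidence that a fatal event normally cannot supply

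*Combined protocol and SAP*

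**What the plan says.** Protocol Section 5.2 (Early Stopping Rules) lists four events. Item 1 is "Death in any subject in which the cause of death is judged to be probably or definitely related to the study drug", as assessed by the treating investigator. Item 2 sets the same two grades for a life-threatening SAE. Item 3 needs two Grade 4 toxicities with those grades. Item 4 needs two allergic reactions, directly related to the drug, that lead to permanent discontinuation. A listed event brings data review by the Medical Monitor and Lead Principal Investigator, suspension of accrual and notification of regulators. The study then stops unless the Medical Monitor and Sponsor agree that it may proceed.

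Section 9.2.3 (Causality Assessment) gives each grade a general description and, for all but *unrelated*, a list of criteria:

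- *Definitely related* applies "if or when it meets all of the following criteria": timing, no other reasonable explanation, and "it follows a known response pattern to treatment with the study treatment".
- *Probably related* covers events that "are felt with a high degree of certainty to be related to the study treatment". Its count is given as "An AE may be considered probable if or when (must have three") of four: timing, no other ready cause, "Disappears or is decreased upon discontinuation of the study treatment", and a known response pattern.
- *Possibly related* uses the same four: "An AE may be considered possible if or when (must have two").
- *Unlikely related* has its own four: "An AE may be considered unlikely if or when (must have two"). Timing and known pattern are negated, but the other two items repeat the *probably* wording without negation.

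Nothing in 9.2.3 says how to treat a criterion that cannot be assessed. Section 12 states that a Data Safety Monitoring Committee does not apply. Section 1.6 mentions a DSMB in connection with West Nile virus but gives it no part in the stopping rules.

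**The concern.** Items 1 and 2 of 5.2 use the same grades, so they appear equally sensitive. They are not, if investigators follow the counts. One of the four routes to *probably related* is improvement after stopping the drug, and a reaction that kills the subject will normally leave no such evidence. The death then has to satisfy every remaining criterion, while a survivor who improves can miss one.

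The criterion most likely to fail is the known response pattern. Section 1.3 reports that no patterns of drug-related toxicity have been seen with leronlimab. An unexpected death soon after dosing, with no other ready cause, is the kind of signal a Phase 2 stopping rule should pick up. At stake is the automatic review and accrual pause. No other item in 5.2 would supply them for a single death graded below *probably related*, and there is no safety committee to do so.

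**Working it through.** The plan gives no operating characteristic for the stopping rules, so there is no figure to reproduce. The check is a count of criteria.

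**Inputs (Section 9.2.3).** Score each criterion 1 if met and 0 if not: c1 timing, c2 no other ready cause, c3 improves on discontinuation, c4 known response pattern.

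- *Definitely*: c1 = c2 = c4 = 1.
- *Probably*: c1 + c2 + c3 + c4 ≥ 3.
- *Possibly*: c1 + c2 + c3 + c4 ≥ 2.
- *Unlikely*: (1 − c1) + c2 + c3 + (1 − c4) ≥ 2.

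**Step 1: which patterns reach *probably* or *definitely*.**

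- c3 = 0 (a death, normally): 1 of 8 patterns, namely c1 = c2 = c4 = 1. These are in substance the *definitely* criteria, so the *probably* grade adds almost nothing.
- c3 = 1 (a survivor who improves): 4 of 8 patterns, namely any two or all three of c1, c2 and c4.
- All survivors: 1 + 4 = 5 of 16. A survivor who does not improve is in the same position as the death.

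These are counts of patterns, not probabilities.

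**Step 2: the case that matters.** Take clear timing, no other ready cause and no known pattern.

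| | c1, c2, c3, c4 | Count toward *probably* (3 needed) | Count toward *unlikely* (2 needed) |
|---|---|---|---|
| Death | 1, 1, 0, 0 | 1 + 1 + 0 + 0 = 2 | 0 + 1 + 0 + 1 = 2 |
| Survivor, improves off drug | 1, 1, 1, 0 | 1 + 1 + 1 + 0 = 3 | 0 + 1 + 1 + 1 = 3 |

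The death satisfies the *possibly* and *unlikely* lists but not *probably*. The survivor satisfies *probably*, so item 2 is open, although the *unlikely* list is met there too.

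**Step 3: other two-criterion deaths.** There are two more with c3 = 0. Timing plus a known pattern, with another possible cause (1, 0, 0, 1), counts 2 toward *probably* and 0 toward *unlikely*. No other cause plus a known pattern, without timing (0, 1, 0, 1), counts 2 and 2, and is clinically implausible.

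**Step 4: other triggers.** Items 2 and 3 require the same grades as item 1. Item 3 needs two occurrences and item 4 needs two allergic reactions. None is met by one death graded *possibly related*.

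**Step 5: after the fix proposed below.** Drop c3 for fatal events and let item 1 include *possibly*. The condition becomes c1 + c2 + c4 ≥ 2, met by 4 of 8 patterns instead of 1 of 8. The Step 2 death then qualifies, provided that *possibly* prevails over *unlikely* when both lists are met.

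**The case against.** The strongest objection is that 9.2.3 is not a scoring algorithm. Each grade opens with a medical description, and the lists say only that an event may be considered to belong there. *Possibly related* is described as unlikely but not excluded, which need not fit a death with clear timing and no other cause. An investigator may grade that death *probably related*, and item 1 then applies. This stands. A reader might infer that such a death must be graded *possibly related*, or that item 1 cannot be reached without a known pattern. The documents support neither, because the lists overlap and leave the grade to judgement. What remains is that the written count for *probably* points away from a grade that the safety trigger depends on.

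Second, a scale should give different grades to different evidence, and improvement off drug is real evidence. That also stands. It makes *possibly related* a defensible grade for a death with another possible cause, so I do not count that case as a defect. The contrast holds only against a survivor who improves. A reaction may also ease before a later death, in which case the criterion can be met.

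Third, little is lost. Section 9.4 sends every SAE to the Medical Monitor within 24 hours and to the IRB, and regulators can be informed through Section 5.3 or expedited reporting (8.7.1). A reader might infer that the death would go unnoticed, and it would not. But none of those routes attaches a data review or an accrual pause.

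Finally, Section 5.3 counts possibly related events as attributable for follow-up. That is no inconsistency, since a wide net for follow-up is compatible with a narrower one for halting a trial.

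**Conclusion.** The point holds in a limited form. If the 9.2.3 counts are followed, a fatal reaction normally reaches *probably related* only with timing, no other ready cause and a known pattern all present. A death lacking only the known pattern meets two of the three criteria required, and the review and pause in 5.2 need not follow. A survivor with the same features who improves off drug meets three.

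This rests on two assumptions: that the investigator uses the counts rather than departing from them, and that improvement off drug was not seen before death. How often such a death would arise cannot be computed from these documents, because expected events are left to the Investigator Brochure (Section 9.6). With 50 subjects randomized 1:1, about 50 / 2 = 25 receive leronlimab, so it would be uncommon. I would class the change as a cheap improvement.

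**What to change.** 1. Extend Section 5.2 item 1 to deaths judged possibly, probably or definitely related.
2. Add to Section 9.2.3, for fatal events only, that criterion (3) is not assessable and is not counted for or against any category, and that the most related category applies if more than one list is met.

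Both are needed. With the first alone, the death in Step 2 could still be graded *unlikely*. The second should stay limited to fatal events, because applying it to all adverse events would regrade other events and alter items 2 and 3 of 5.2 and the causality tables. The un-negated items in the *unlikely* list deserve their own correction, but that is a separate matter.

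The cost is an occasional extra review, accrual pause and regulator notification, with the study stopped by default unless the Medical Monitor and Sponsor agree to proceed, as 5.2 already allows. If a reaction did ease before a later death, that evidence would no longer count. With timing and no other ready cause the death would still be *possibly related*, and item 1 would still apply. Dosing, sample size and efficacy analyses are unchanged.

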3.1. STUDY CENTER

Up to 5 multinational centers. Centers must have the capability of implementing appropriate infection-control measures to prevent infection of study staff and others who share the clinical site space.

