If Visit 2 (V2) takes place on the same day as the Screening Visit (V1), scheduled assessments performed under screening (V1) do not need to be repeated at V2. Subjects will be given a diary to record all symptoms daily throughout the entire treatment period starting at baseline.

Treatment Groups

IP Study Dosage **Dosing Frequency and Amount** Form concentration

Table 4-1:

Route of Drug Administration Parenteral 2 injections of PRO 140 (2 X 2 mL/inj.) PRO 140 175 mg/mLSC injection (700 mg)solution per week on opposite sides of abdomen 2 injections of placebo (2 X 2 mL/inj.) Parenteral 0 mg/mLSC injection Placebo solution per week on opposite sides of abdomen

At V2, subjects will be randomized to receive leronlimab (PRO 140) or placebo which will be administered subcutaneously weekly at V2, V4, V6, V8, V10, V12, V14, and V16.

The following assessments will be performed at V4, V6, V8, V10, V12, V14, V16, and V17(EOT): vital signs, pulse oxygen saturation, physical examination, electrocardiogram (ECG (V17 only), PROMIS® Fatigue Scale, PROMIS® Cognitive Function- Short Form 4a, PROMIS® Sleep Disturbance – Short Form 4a, Global Health Assessment (V17 only), blood sample collection for routine serum biochemical, hematologic, coagulation and urine laboratory assessments (V10 and V17). CD4+ and CD8+ T cell count and serum cytokine and chemokine levels (V10 and V17), assessment for the requirement of hospitalization and patient compliance to daily diary completion will be checked by the site staff.

Additionally, telephone or video contact visits will be performed 3 days (±1 day) after each treatment administration visit. The requirement of hospitalization and patient compliance to daily diary completion will be checked during V3, V5, V7, V9, V11, V13, and V15 via telephone.

Adverse events and concomitant medications will be monitored throughout the study.

Follow Up Period (4 weeks after EOT± 3 days)

Follow-up visit (V18) will be performed 4 weeks after the End of Treatment (EOT) visit. The following assessments will be performed at V18: vital signs, physical examination, pulse oxygen saturation, blood sample collection for immunophenotypic biomarker analysis, assessment for the requirement of hospitalization, review of adverse events and concomitant medications.

Note: During visits conducted at the study clinic, subjects and site personnel will use appropriate protective gear (e.g., masks, gloves) to prevent the spread of the infection.

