5.3. REMOVAL OF SUBJECTS FROM STUDY TREATMENT AND/OR STUDY AS A WHOLE

Subjects can be taken off the study treatment and/or study as a whole at any time at their own request, or they may be withdrawn at the discretion of the investigator for safety, behavioral or administrative reasons. In the case that a subject is removed from the study due to safety reasons, the FDA and other global regulatory authority will be notified. The reason(s) for discontinuation must be clearly documented on the appropriate eCRF and may include:

- Subject voluntarily withdraws from treatment (follow-up permitted)
- Subject withdraws consent (no follow-up permitted)
- Subject is unable to comply with protocol requirements

CONFIDENTIAL Page 54 of 101

- Subject experiences unacceptable toxicity
- Treating physician determines that continuation on the study would not be in the subject's best interest
- Subject becomes pregnant
- Subject becomes lost to follow-up (LTF)
- Subject will be withdrawn from the study if 2 consecutive doses of study drug are missed
- Subject manifesting Grade 4 or Grade 3 toxicity attributable to the Leronlimab (PRO 140)

If a subject fails to return for the scheduled study visit or is discontinued from the study, an attempt will be made to determine the reason(s). If the subject is unreachable by telephone, a registered letter will be sent to the subject requesting that he/she contact the clinic.

All patients with an ongoing SAE or AE attributable (definitely, probably, or possibly related) to the study treatment at the Post-Study (Follow-up) Visit (scheduled or premature) must be followed until the event is resolved (with or without sequelae) or deemed stable.

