11.3. MODIFICATION OF PROTOCOL

The Investigator will not modify or alter this protocol without first obtaining the concurrence of the Sponsor. Approval by the Investigator's IRB must also be obtained prior to implementation of the change, with two exceptions:

- 1. When necessary to eliminate apparent immediate hazard to the subject; or
- 2. When the modification does not involve the subject's participation in the trial.

CONFIDENTIAL Page 81 of 101

An amendment may also require modification of the informed consent form. The Investigator will provide an approval letter for the amendment and revised informed consent form, if applicable, to the Sponsor. An amendment must be provided in writing and it must be dated by both the Sponsor and the Investigator. If necessary, the Sponsor will submit protocol amendments to FDA and other appropriate regulatory authorities and notify other Investigators using this protocol.

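### While a stopping event is under review, Section 5.2 of the protocol suspends accrual but nothing requires weekly dosing of subjects already randomised to be held

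*Combined protocol and SAP*

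**What the plan says.** Protocol Section 5.2 lists four triggers:

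1. a death probably or definitely related to study drug;
2. a life-threatening SAE with the same attribution;
3. two Grade 4 toxicities with the same attribution;
4. two Grade 2 or higher allergic reactions directly related to study drug that lead to permanent discontinuation.

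The Medical Monitor and the Lead Principal Investigator review the data. In the meantime "patient accrual will be suspended pending further review", and regulators are notified. The study is then stopped unless, after review, "the medical monitor and Sponsor, agree to allow the study to proceed". Regulators are to be consulted on any amendment "before restarting the trial if a stopping rule is met".

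Study drug is "administered subcutaneously weekly at V2, V4, V6, V8, V10, V12, V14, and V16", which is 8 doses from Day 0 to Day 49 (Section 4). Section 5.3 adds that subjects may come off treatment at their own request or "they may be withdrawn at the discretion of the investigator for safety, behavioral or administrative reasons". It also says: "Subject will be withdrawn from the study if 2 consecutive doses of study drug are missed".

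**The concern.** Subjects already on treatment are the ones exposed to the suspected harm. The interim action that 5.2 spells out acts on people who have not yet received anything. A site following the text literally after a related death would stop randomising and could still give the next scheduled injection to everyone else.

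The gap is widest at the end of recruitment. After the 50th randomisation there is no accrual left to suspend, yet the last subject's dosing runs to Day 49, seven more weeks. No time limit is set for the review. Section 12 states that a data safety monitoring committee is not applicable, so no independent body would call a dosing hold, and the written rule carries more weight.

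**Working it through.** **Step 1: look for a dosing hold elsewhere.** The plan gives no figure to reproduce, so the main check is a reading of every place that could supply the missing requirement.

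| Place | What it provides | Holds dosing of other subjects during a 5.2 review? |
|---|---|---|
| 5.2 | Accrual suspended; study stopped by default, subject to the review | Not stated |
| 5.3 | Withdrawal of individual subjects at investigator discretion | No; permissive, subject by subject |
| 6.1.5, Tables 6-3 and 6-4 | Dose withheld or discontinued by CTCAE grade | No; a subject's own toxicity only |
| 9.4, 9.5 | SAE to the Medical Monitor within 24 hours; follow-up of the event | No |
| 11.3 | No prior IRB approval needed for a change "When necessary to eliminate apparent immediate hazard to the subject" | No; allows a pause, does not require one |
| 12 | No safety monitoring committee | No |
| SAP | No stopping or dosing-hold rule | No |

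A pause is therefore possible under the plan, but nothing orders it.

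**Step 2: scale.** This is illustrative, because the documents state neither accrual duration nor review length.

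Inputs from the protocol: 50 subjects (8.3) and 8 weekly doses each (Table 6-1), so 50 × 8 = 400 planned doses.

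Assumptions: even accrual over A = 10, 20 or 30 weeks; exact 7-day dosing with no dropout; review length R = 3, 7 or 14 days; event at 25%, 50%, 90% or 100% of accrual.

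Subject i (1 to 50) starts on day s = (i − 1) × 7A/49 and is due doses at s + 7j, for j = 0 to 7. With the event at day t, count the doses due after t and up to t + R among subjects with s ≤ t.

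Further doses allowed, with the event at 25 / 50 / 90 / 100% of accrual:

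| Review | A = 10 weeks | A = 20 weeks | A = 30 weeks | Range | Share of 400 |
|---|---|---|---|---|---|
| 3 days | 4 / 11 / 14 / 14 | 5 / 7 / 8 / 7 | 6 / 5 / 6 / 5 | 4 to 14 | 1% to 3.5% |
| 7 days | 13 / 25 / 35 / 35 | 13 / 17 / 18 / 18 | 12 / 11 / 12 / 12 | 11 to 35 | 2.75% to 8.75% |
| 14 days | 26 / 50 / 65 / 65 | 26 / 32 / 33 / 33 | 22 / 21 / 22 / 22 | 21 to 65 | 5.25% to 16.25% |

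Hand check of the largest cell (A = 10, R = 14, event at full accrual): 35 subjects still have a dose due, and 5 of them have only one left. The first week gives 35 doses and the second 35 − 5 = 30, so 65 in total. With 1:1 allocation about half of any of these counts is placebo.

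**The case against.** The best counter-argument is that 5.2 already halts the trial. Stopping follows from the criterion being met, proceeding needs a positive agreement, and a trial that is still dosing does not need restarting. This has force: it shows that the text is ambiguous rather than permissive. A reader might infer that the sponsor meant dosing to continue during a review, and the documents do not support that. But the stop depends on the outcome of the review, and the restart wording belongs to a sentence about consulting regulators on an amendment. Neither tells a site to withhold the next injection.

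A second tempting inference is that each of "Up to 5 multinational centers" would decide for itself. The documents point the other way. The review and the decision to proceed sit with central roles, and SAEs must reach the Medical Monitor within 24 hours of the investigator becoming aware. With doses 7 (±1) days apart, the Medical Monitor will often know before most subjects' next injection. That speeds a decision; it does not require a hold.

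A third is that a two-week hold would force withdrawals under the two-consecutive-dose rule in 5.3. That needs a hold to be called, to span two dose visits, and ordered holds to count as missed. Tables 6-3 and 6-4 use a different word, withhold, for ordered interruptions, so 'missed' more naturally means a dose not attended. The rule is silent on the point, which justifies a precautionary sentence but not a count of affected subjects.

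Finally, a dosing halt for everyone may be too much for trigger 4. That is fair, and the fix allows for it.

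**Conclusion.** The point holds as a gap in a safety rule that should be closed. For the review period 5.2 orders only an accrual suspension, no other text supplies a dosing hold for subjects already randomised, and after the 50th randomisation the ordered action has no effect. This conclusion rests on the wording alone.

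The size is conditional on a trigger occurring, and the documents give no probability for that. Review length drives the result: at most 14 further doses for 3 days, 35 for 7 days and 65 for 14 days under the fastest accrual assumed. No single row is a full range, since a longer review or a different accrual pattern would change it.

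**What to change.** - **5.2, the hold.** In the sentence that suspends accrual, add study drug administration to all subjects. State that dosing resumes only once the Medical Monitor and Sponsor have documented their agreement to proceed, and that diary entries and safety visits continue during the hold. Apply this at minimum to triggers 1 to 3; the sponsor can decide whether trigger 4 warrants it.
- **5.3, precaution.** Add that doses withheld under a 5.2 hold do not count as missed for the two-consecutive-dose withdrawal rule.

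The cost is a few sentences and no new committee or staff. The downside is that a false alarm interrupts dosing for everyone on treatment, at about one dose per subject per week of review; a 14-day hold takes up to 2 of a subject's 8 doses. That could dilute the comparison through Day 56. The dilution has not been calculated.
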